4.2 Statistical and Analytical Methods

4.2.1 Analysis Populations and Analysis Groups

Population of Patients Enrolled [EP]

The population of patients enrolled comprises all patients who voluntarily sign and date an informed consent prior to inclusion into the study and data were captured in the eCRF.

Target Population [TP]

Patients will be included if the following applies:

- Age at least 18 years
- Confirmed CHC with genotype 1 and/or 4 only, receiving combination therapy with the interferon-free ABBVIE REGIMEN \pm RBV. The prescribed ABBVIE REGIMEN needs to be known.
- Have voluntarily signed and dated an informed consent prior to inclusion into the study
- Must not be participating or intending to participate in a concurrent interventional therapeutic trial

Core Population [CP]

The core population is defined as all patients of the target population (TP) (definition see above), who are adequately treated according to the standard of care and within local label recommendations for their specific disease characteristics (cirrhotic status, genotype). The following patients will be excluded from the CP:

- Patients with unknown fibrosis status
- Cirrhotic patients with genotype 1a not receiving ribavirin
- Patients with genotype 1 for whom 2DAA instead of 3DAA is prescribed
- Patients with genotype 4 not receiving RBV

Non-Core Population [NCP]

Patients in the TP who are not in the CP.

Core Population with Sufficient Follow-up [CPSFU {12, 24}]

In addition, the core population with sufficient follow-up data regarding SVR12 or SVR24, respectively, is defined as all CP patients,

- who have evaluable HCV RNA data ≥ 70 days or >126 days, respectively, after the last actual dose of the ABBVIE REGIMEN
- or a HCV RNA value ≥ 50 IU/mL at the last measurement
- or had HCV RNA <50 IU/mL at the last measurement, but no HCV RNA measurement ≥ 70 days or >126 days, respectively, after the last actual dose of the ABBVIE REGIMEN due to reasons related to safety (e.g. dropped out due to adverse event) or virologic failure (e.g. virologic failure such as relapse is reported in the electronic case report form (eCRF) but date and value of the corresponding HCV RNA test is missing).

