4.2.2 Definition of Baseline and Visit Time Windows

This observational study covers three documentation periods, see Figure 1. An overview of data to be collected throughout the study is summarized in Table 2.

Table 2 - Data Documentation Schedule

Assessment/ Procedure (only available data to be collected; no diagnostic or monitoring procedures to be applied to the patients apart from those of routine clinical practice)	Baseline	Treatment Period			Post-treatment (PT) Period		
		On-treatment visits	Mid treatment visit for pts receiving 24 weeks of therapy	EoT ^b	Early PT visit	SVR 12 visit	SVR 24 visit
Informed Consent	X ^a						
Demographic information	X						
IL28B	X						
Relevant CHC disease characteristics	X						
Liver fibrosis stage	X						
CHC treatment history	X						
HCV genotype and subtype	X						
HCV RNA samples	X	X	X	X	X	X	X
Clinical chemistry and hematology	X	X	X	X	X	X	X
ABBVIE REGIMEN initiation documentation	X						
ABBVIE REGIMEN adherence		X	X	X			
Concomitant medication	X	X	X	X			
Relevant medical history, co-morbidities	X						
sAE, AE and pregnancy reporting	X	X	X	X	X ^c	X ^d	X ^d
For patients receiving RBV: Evidence, in accordance with local label, that female patient or female partner of male patient is not pregnant	X						
Viral resistance sample	X			X		X	X
Patient questionnaires – PAM-13, BMQ 18-item	X			X			
PSP evaluation		X	X	X	X	X	

Abbreviations: EoT = End of Treatment (at Week 12 or 24 or at premature discontinuation),
PT = Post-Treatment

a Written informed consent must be obtained before any data documentation in the eCRF

b Patients who prematurely discontinue should return to the site to document EoT data

c Tolerability documentation until PT week 4

d Pregnancy reporting for patients treated with DAA plus RBV

In accordance with the non-interventional nature of the study all HCV RNA measurements will be performed at the sole discretion of the physician and all HCV RNA measurements have to be entered into the eCRF. All recorded HCV RNA values will be assigned to appropriate time points (baseline, on-treatment visits, EoT visit, post-treatment visits) as follows:

Table 3 - Analysis Time Windows for HCV RNA

Phase	Time point	Time Window
Pre-Treatment	Baseline	Last value prior to start of study treatment (i.e. \leq study day 1)
On-treatment		Study day during treatment period ^{^#} (Study day 1 = first treatment day)
Treatment Week	4 (RVR*)	15 - 42 [^]

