EoT	Actual EoT	Study day of last dose# (28 days prior to last dose - 7 days post last dose)
Post Treatment	12 weeks (SVR 12 window)	\geq 70-126 days post last dose
	24 weeks (SVR24 window)	127-210 days post last dose

[^]values must also be \leq 7 days post last dose

\geq study day 2

*RVR = rapid virological response

All reported safety laboratory test results will be assigned to one of the time points using the time windows specified in the table below.

Table 4 - Analysis Time Windows for Safety Laboratory Data

Phase	Time point	Time Window
Pre-Treatment	Baseline	Last value prior to start of study treatment (i.e. \leq study day 1)
Treatment Weeks	4 (day 29)	Study day during treatment period (Study day 1 = first treatment day)
	8 (day 57)	15 – 42 [^]
	12 (day 85)	43 – 70 [^]
	16 (day 113)	71 – 98 [^]
EoT	Actual EoT	Study day of last dose# (28 days prior to last dose - 7 days post last dose)
Post Treatment	4 weeks (28 days post last dose)	8– 56 post last dose
	12 weeks (84 days post last dose)	57 – 126 days post last dose
	24 weeks (168 days post last dose)	127 – 252 days post last dose

[^]values must also be \leq 7 days post last dose

\geq study day 2

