4.2.3 Handling of missing data

No data will be imputed for any effectiveness or safety analyses except for the analyses of the HCV RNA endpoints and certain PRO endpoints. The discussion of missing data imputation for the PRO endpoints is included in section 4.2.7.2.3.

HCV RNA values will be selected for an RVR, EOTR and SVR analysis based on visit windows as defined in Table 3. When there is no HCV RNA value in a visit window based on defined visit windows, the closest values before and after the window, regardless of the value chosen for the subsequent and preceding window, will be used for the flanking imputation described below. For analysis of RVR, EOT and SVR, if a subject has a missing HCV RNA value at a post-Day 1 visit but with undetectable or unquantifiable (\leq 50 IU/mL) HCV RNA levels at both the preceding value and succeeding value, the HCV RNA level will be considered undetectable or unquantifiable, respectively, at this visit for this subject. In addition, if a subject has an unquantifiable HCV RNA level at the preceding value and an undetectable HCV RNA level at the succeeding value, or vice versa, the HCV RNA level will be imputed as unquantifiable at this visit for this subject.

For analyses of RVR, subjects still missing a value for the visit after flanking imputation will be imputed as a failure. For EoTR and SVR analysis, if there is no value in the appropriate window after flanking imputation but there is an HCV RNA value after the window, then it will be imputed into the EoTR or SVR window respectively. Subsequent to this flanking imputation, if a subject is missing a value for the visit window associated with the analysis, the subject will be imputed as a visit failure (i.e., not undetectable or unquantifiable).

If a subject starts another treatment for HCV, then all HCV RNA values for this subject measured on or after the start date of the new HCV treatment will be excluded from analyses. The subject will be considered a failure for summaries of viral response at all time points after the start of the new HCV treatment.

Due to the non-interventional nature of this study several different methods for determination of the HCV RNA value can be applied. For the purpose of the statistical analysis, a HCV RNA measurement is considered ≤ 50 IU/mL,

- if a PCR test was used

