4.2.7.2 Secondary Variables

4.2.7.2.1 Secondary Effectiveness Variables

Response

For the other response rates (i.e. SVR24, EoT response rate, relapse rate), the simple percentage of patients and a two-sided 95% confidence interval (CI) of the percentage will be computed (based on the Wilson's score method) as well. The EoT response rate will be reported for CP and the SVR24 rate will be reported for the respective CPSFU, stratified by genotype and cirrhosis status and overall. The relapse rates will be estimated stratified by SVR window (i.e. during SVR12 window=relapse₁₂, during SVR24 window=relapse₂₄) and stratified by genotype

and cirrhosis status and overall in patients of the CP with EoT response who fulfilled the following criteria:

- completed treatment as defined previously,
- had at least one HCV RNA measurement ≥ 70 days post-treatment or was a treatment failure between EoT and 70 days post-treatment.

Viral breakthrough rates [defined as at least one documented HCV RNA <50 IU/mL followed by HCV RNA ≥ 50 IU/mL during treatment] will be estimated overall and stratified by genotype and cirrhosis status in all patients of the CP, who have at least one undetectable or unquantifiable, on-treatment HCV RNA measurement and at least one on-treatment or EoT measurement thereafter.

Non-Response

In another table, the numbers and the percentages of the SVR12 non-responder categories and responder will be summarized for CP patients, overall and stratified by genotype and cirrhosis status. The following SVR12 non-response categories will be considered:

- On-treatment virologic failure (breakthrough [defined as at least one documented HCV RNA <50 IU/mL followed by HCV RNA ≥ 50 IU/mL during treatment] or failure to suppress [each measured on-treatment HCV RNA value ≥ 50 IU/mL])
- Relapse (defined as HCV RNA <50 IU/mL at EoT or at the last on-treatment HCV RNA measurement followed by HCV RNA ≥ 50 IU/mL post-treatment and completed treatment as defined previously)
- Death and none of the above
- Premature study drug discontinuation with no on-treatment virologic failure and none of the above
- Insufficient virological response, other than those mentioned above (patients for whom insufficient virological response was reported, or who had HCV RNA ≥ 50 IU/mL post EoT and no HCV RNA test on treatment) and none of the above
- Missing SVR12 data and/or none of the above criteria

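### The SAP gives relapse24 the same follow-up criterion as relapse12, so its denominator includes patients who cannot show a new relapse on days 127-210, and the rate is diluted

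*SAP*

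**What the plan says.** In SAP 4.2.7.2.1, "The relapse rates will be estimated stratified by SVR window": relapse12 is relapse during the SVR12 window and relapse24 is relapse during the SVR24 window. Both are estimated in core-population patients with EoT response who completed treatment and who "had at least one HCV RNA measurement ≥ 70 days post-treatment or was a treatment failure between EoT and 70 days post-treatment". No second criterion is given for the later window. Each rate gets a Wilson 95% interval.

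SAP Table 3 (section 4.2.2) sets the SVR12 window at days 70-126 after the last dose and the SVR24 window at days 127-210. SAP 4.1.2 defines relapse as HCV RNA below 50 IU/mL at EoT followed by a value of 50 IU/mL or more, with no lower time limit.

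For SVR24 the SAP does separate the windows: "the SVR24 rate will be reported for the respective CPSFU". That population (section 4.2.1) consists mainly of core patients "who have evaluable HCV RNA data ≥ 70 days or >126 days, respectively, after the last actual dose of the ABBVIE REGIMEN", plus defined failures.

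Protocol 9.7.3.3 asks only that EoT responders in the relapse analysis have sufficient post-treatment HCV RNA measurements. It sets no day limit, so the 70-day criterion is the SAP's own.

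**The concern.** A rate needs a denominator of people in whom the event could have been seen. Take a completer with EoT response whose last test was negative on day 84. The day-84 value satisfies the 70-day criterion, so this patient is in the relapse24 denominator with no value on days 127-210. A patient who relapsed on day 84 is in it too, although that relapse belongs to the earlier window.

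Such patients are to be expected. The study does not schedule testing: "all HCV RNA measurements will be performed at the sole discretion of the physician". SAP 4.2.5 treats a patient as not completing the study only if there is no HCV RNA test at 10 weeks or later, so a patient may complete the study with no later test.

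What is at stake is how relapse24 is read. It would look like the frequency of late relapse, but part of a low figure could simply reflect missing late tests, and its interval would be based on more patients than were observed.

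**Working it through.** **Figure to reproduce.** None. The documents give no expected relapse rate, relapse denominator or share of untested patients. The inputs below are assumptions, except the windows and definitions.

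**Who is in the denominator, and who can have an event.** All are completers with EoT response; days are counted from the last dose.

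| HCV RNA after treatment | In SAP relapse24 denominator? | New observed event possible on days 127-210? |
|---|---|---|
| Day 84 <50, no later test | Yes | No |
| Day 84 ≥50 | Yes | No, already relapsed |
| Day 30 ≥50 | Yes, as an early failure | No, already relapsed |
| Day 84 <50, day 168 tested | Yes | Yes |

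Only the last row belongs in a late-relapse rate.

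**Size of the dilution.** Assume D = 400 in the SAP denominator and 12 relapsed by day 126, which leaves L = 400 − 12 = 388. Let t be the share of these tested on days 127-210, and r = 1% the late relapse rate among those tested.

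- SAP rate = L × t × r / D
- Rate among those tested = (L × t × r) / (L × t) = r
- Ratio of the two = (L / D) × t = 0.97 × t, whatever r is

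| t | Tested | Expected events | SAP relapse24 | Among those tested |
|---|---|---|---|---|
| 0.8 | 310.4 | 3.10 | 0.78% | 1.0% |
| 0.6 | 232.8 | 2.33 | 0.58% | 1.0% |
| 0.4 | 155.2 | 1.55 | 0.39% | 1.0% |

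Most of the dilution comes from the untested patients (factor t). Earlier relapsers contribute only the factor 0.97.

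**Interval.** At t = 0.6, rounding to 2 events, the Wilson 95% interval is 0.14-1.80% for 2/400 and 0.24-3.08% for 2/233.

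**Failures before day 70.** The criterion admits them to the denominator, but the label for relapse12 ties events to days 70-126. If 4 of the 12 relapses were found before day 70 with no retest (assumed), relapse12 is 12/400 = 3.0% when they count and 8/400 = 2.0% when they do not.

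**The case against.** **One cohort, relapses sorted by time of detection.** The SAP may intend a single set of EoT responders in which each relapse is classified by window. The two proportions would then add up to total detected relapse, and the SAP nowhere claims a rate among patients tested. This is a fair reading. Even so, relapse24 remains diluted by missing late tests, and the text does not ask for the number tested. The layouts in Part II of the SAP are not among the documents, so whether they show that number cannot be judged. An SVR24 visit is also in the documentation schedule, so the untested share may be small; the documents do not say.

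**Missing counted as relapse.** A reader might infer that untested patients become relapses, because under SAP 4.2.3 "if a subject is missing a value for the visit window associated with the analysis, the subject will be imputed as a visit failure". In the example this would give (388 × t × 0.01 + 388 × (1 − t)) / 400 = 20.2%, 39.4% or 58.6%. The documents do not support this. Section 4.2.3 applies its window rules to RVR, EoT response and SVR, not to relapse, and relapse requires a value of 50 IU/mL or more, which a missing value is not. The plan should say so, but these figures are not a forecast.

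**Entry depending on the outcome.** A reader might also infer that relapsers are systematically removed. Where the EoT window ("28 days prior to last dose - 7 days post last dose") is empty "but there is an HCV RNA value after the window, then it will be imputed into the EoTR or SVR window respectively". A completer suppressed on treatment would then become an EoT non-responder if the next value is positive and a responder if it is negative. This holds only if EoT response for the relapse rate includes imputed status, which the SAP does not state. The effect is also small. With a true rate of 3%, 5-20% lacking an EoT value, and half to all of those relapsers positive at the next test, 400 × 0.03 × 0.05 × 0.5 = 0.3 to 400 × 0.03 × 0.20 × 1 = 2.4 relapsers per 400 are lost. The rate becomes 2.93% to 2.41%, inside the Wilson interval for 12/400 (1.7-5.2%). The possible mismatch with the non-response table, which also accepts the last on-treatment value, comes from the two relapse definitions already in protocol 9.7.3.2.

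**Early failures.** Admitting them to the denominator makes sense only if their event can count, and SAP 4.1.2 sets no lower limit. One clarifying sentence is enough.

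**Conclusion.** The mismatch follows from the SAP's wording and needs no assumption: one criterion starting at day 70 serves a window that starts at day 127. On the ordinary reading, with relapse as a measured value, the error in relapse24 is downward, by a factor of about 0.97 × t in the example. The size depends on the untested share and the number of earlier relapses, neither of which the documents give. In absolute terms it is a fraction of a percentage point when late relapse is near 1%, and the two illustrative intervals overlap.

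The text does not support a relapse24 of 20% or more, or a material loss of relapsers through EoT imputation. Relapse is a secondary descriptive endpoint; primary SVR12 and the sample size are untouched. The change is still worth making: relapse is a listed endpoint with its own table and intervals, the correction is cheap, and the SAP already applies the same principle to SVR24.

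**What to change.** Amend the relapse paragraph of SAP 4.2.7.2.1:

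- **Relapse24.** Denominator: EoT responders who completed treatment, had no relapse by day 126 and have an observed HCV RNA value on days 127-210, whatever its result. Event: first value ≥50 IU/mL in that window.
- **Relapse12.** State that a documented value ≥50 IU/mL after EoT and before day 70 counts as an event.
- **Imputation.** State that the missing-as-failure and back-fill rules of 4.2.3 neither create nor remove relapse events. Keep the 4.2.3 handling of values measured after the start of a new HCV treatment.
- **Display.** Print the numbers tested and untested beside each rate. Footnote that a first positive on days 127-210 with no value on days 70-126 may be an earlier relapse detected late.
- **Sensitivity count only.** Report completers with no observed EoT-window value whose last on-treatment value was <50 IU/mL and who were later ≥50 IU/mL, so that the relapse and non-response tables can be reconciled. This should not enter the main definition, because it would change the EoT-based endpoint in protocol 9.7.3.2 and SAP 4.1.2.

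The cost is SAP wording and derivation code, with no new data. The relapse24 denominator shrinks and its interval widens: in the 60%-tested example from 400 to about 233 patients, with the upper limit for 2 events moving from 1.80% to 3.08%. The reported rate may look slightly less favourable.

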4.1.2 Secondary Parameters

The secondary effectiveness endpoints are:

- The percentage of patients with virological response (HCV RNA <50 IU/mL) at EoT (defined as last intake of ABBVIE REGIMEN or ribavirin)
- The percentage of patients with relapse (defined as HCV RNA <50 IU/mL at EoT followed by HCV RNA ≥50 IU/mL)
- Sustained virological response 24 weeks after EoT (SVR24, i.e. patients with HCV RNA < 50 IU/mL 24 weeks after EoT)
- The number and percentage of patients meeting each and any of the following SVR12 non-response categories:
 - On-treatment virologic failure (breakthrough [defined as above] or failure to suppress [each measured on-treatment HCV RNA value ≥50 IU/mL])
 - Relapse (defined as HCV RNA <50 IU/mL at EoT or at the last on-treatment HCV RNA measurement followed by HCV RNA ≥50 IU/mL post-treatment for subjects who complete treatment [not more than 7 days shortened])
 - Premature study drug discontinuation with no on-treatment virologic failure
 - Missing SVR12 data and/or none of the above criteria

Further secondary variables are:

- Type of treatment regimen (\pm Dasabuvir, \pm RBV, intended and actual combination, dose and duration)
- Adherence
 - Percentage of the DAA dose taken in relation to the target dose of DAA (cumulative dose taken divided by target dose in percent)
 - Percentage of the RBV dose taken in relation to the target dose of RBV (cumulative dose taken divided by target dose in percent)
 - Percentage of missed RBV treatment days in relation to the target number of RBV treatment days
- Co-morbidities and concomitant medication
- Serious and non-serious adverse events and pregnancy occurrences
- PAM-13, BMQ, PSP satisfaction and utilization questionnaires
- Resistant virus variants at post-baseline time points compared to baseline

No data will be imputed for any effectiveness or safety analyses except for the analyses of the HCV RNA endpoints and PRO questionnaires (if applicable). For further details see sections 4.2.3 and 4.2.7.2.3, respectively.

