In addition, univariate and multiple logistic regression (MLR) analysis will be performed to investigate the association of the use of the PSP, the patient satisfaction variables of the PSP questionnaires with treatment completion. First the use of PSP will be analyzed in all CP patients. The patient satisfaction will only be analyzed in patients who participated in the PSP. The satisfaction categories pre-specified above could be combined in the analyses if this is supported by the data (e.g. very good and good vs satisfactory vs poor). Furthermore, continuous variables can be replaced by categorical variables.

Use of the PSP is defined as taking part in PSP. For all satisfaction variables the worst case before last intake is considered. 'Poor' will be used as reference value. Patients will be considered to have completed treatment when the actual duration of the ABBVIE REGIMEN is not shortened for more than 7 days.

If the percentage of patients with available data for a variable is lower than 80% of the patient group analyzed, then this variable will not be considered in the MLR analysis.

These analyses will be of exploratory nature and data driven. Backward selection procedures will be applied to generate the final MLR models. A p-value <0.05 will be used for the covariates to stay in the model in a backward elimination step.

Patient Activation Measure – (PAM-13)

The Patient Activation Measure (PAM) 13 is a measure used to assess the patient knowledge, skill, and confidence for self-management. The PAM-13 item scale is a measure used to assess the patient knowledge, skill, and confidence for self-management. Each of the 13 items can be answered with one of four possible response options, which are “disagree strongly” (1), “disagree” (2), “agree” (3), “agree strongly” (4).

The scoring will be done by Insignia Health. If there are less than nine items answered, no summary score will be calculated.

A summary table will show descriptive statistics (n, mean, median, SD, minimum and maximum) of the score for baseline and the post-baseline time points, as well as changes from baseline, by cirrhosis status and treatment regimen. In addition, analysis of covariance (ANCOVA) will be applied to investigate the effect of the different ABBVIE REGIMENS (\pm RBV) by cirrhosis status on the score using the corresponding baseline value as covariate.

Beliefs Medication Questionnaire – (18-item BMQ)

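### Failure to suppress has no minimum time on treatment, so a lone early HCV RNA value of 50 IU/mL or more files early stops and deaths as on-treatment virologic failure

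*SAP*

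**What the plan says.** SAP 4.2.7.2.1 sorts SVR12 non-responders in the core population (CP) by reason. The first category is on-treatment virologic failure: either breakthrough, or "failure to suppress [each measured on-treatment HCV RNA value" at or above 50 IU/mL. SAP 4.1.2 repeats it ("On-treatment virologic failure (breakthrough [defined as above] or failure to suppress [each measured on-treatment HCV RNA value" at or above 50), and protocol 9.7.3.2 has the same rule. None of the three sets a minimum exposure, a minimum number of tests or an earliest day.

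SAP Table 3 takes on-treatment HCV RNA from the "Study day during treatment period", and its footnotes admit values from study day 2 up to 7 days after the last dose. SAP 4.2.2 adds that "all HCV RNA measurements will be performed at the sole discretion of the physician".

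Two lower categories are explicitly subordinate: "Death and none of the above" and "Premature study drug discontinuation with no on-treatment virologic failure and none of the above". Relapse needs a value below 50 at EoT or "at the last on-treatment HCV RNA measurement followed by HCV RNA" of 50 or more post-treatment, plus completed treatment, which SAP 4.2.7.2.2 describes as: "actual duration of the ABBVIE REGIMEN is not shortened for more than 7 days". Relapse has no clause excluding patients already in the first category. The insufficient-response category takes patients with that outcome reported, or with a positive post-EoT value and no on-treatment test. The last category joins missing SVR12 data to the remainder with an and/or.

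**The concern.** HCV RNA has to fall a long way before it passes 50 IU/mL. A value taken in the first days or weeks can be at or above 50 in a patient who is responding. If no later on-treatment test exists, that one value satisfies the definition, because each measured value is then the single early one.

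The table is meant to separate failure of the drug from poor tolerability, death and loss to follow-up. As written, an early stop for an adverse event can be reported as a virologic failure because of when the site happened to test. The disposition table on reasons for stopping treatment (SAP 4.2.5) could then give an adverse event as the reason for the same patient.

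**Working it through.** **Plan figures, for scale only.** No figure is attached to the definition itself. Clopper-Pearson limits for 417 patients at 90% reproduce as 86.71 to 92.71, width 6.00, as in SAP Table 1. Enrolment is 417 / 0.95 = 438.9, so 439 against 440 stated.

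**Worked patients.** The SAP 4.2.7.2.1 rules were applied literally to hypothetical SVR12 non-responders. All values are in IU/mL.

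| Patient | Result as written |
|---|---|
| (a) Adverse-event stop on day 12; only value day 10 = 300 | On-treatment virologic failure; barred from premature discontinuation |
| (b) Early drop-out; only value day 15 = 120 | Same as (a) |
| (c) Completer; only value day 15 = 120; lost to follow-up | On-treatment virologic failure, and also meets missing SVR12 data |
| (d) Completer; only on-treatment value day 15 = 120; no EoT test; post-treatment 100,000 | On-treatment virologic failure |
| (e) As (d), but below 50 at post-treatment week 4, then 100,000 | On-treatment virologic failure and relapse |
| (f) Death on day 14; only value day 10 = 300 | On-treatment virologic failure; barred from death |
| (g) Day 15 = 120, EoT below 50, post-treatment 100,000 | Relapse only (correct) |
| (h) Adverse-event stop on day 40; day 10 = 300, day 30 below 50 | Premature discontinuation only (correct) |

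Imputation does not rescue (a) to (f), because the definition speaks of measured values. In (d), SAP 4.2.3 carries the later positive value back into the empty EoT window, which also blocks relapse. The insufficient-response category does not take (d) unless that outcome was reported, because an on-treatment test exists. In (e), the value carried back is below 50, so relapse is met as well.

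**Size per patient.**
- As a share of the CP: 1 / 417 = 0.24 points.
- Non-responders at 90% SVR12: 417 × 0.10 = 41.7, about 42. One patient is 1 / 41.7 = 2.4 points of them.
- Non-responders at 95% SVR12: 417 × 0.05 = 20.85, about 21. One patient is 1 / 20.85 = 4.8 points of them.
- If five patients were affected (an assumption): 5 / 417 = 1.2 points of the CP, or 12.0 to 24.0 points of the non-responders.

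**Can an early value of 50 or more occur in a responder?** From the SAP's lowest and highest baseline cut-offs, the fall needed is log10(400,000 / 50) = 3.9 to log10(10,000,000 / 50) = 5.3. The documents give no rate of decline. Assume a drop of A = 2.5 to 3.5 log10 by day 2, then s = 0.1 to 0.3 log10 per day. The crossing day is 2 + (fall needed − A) / s:
- Fastest: 2 + (3.90 − 3.5) / 0.3 = 3.3.
- Slowest: 2 + (5.30 − 2.5) / 0.1 = 30.0.

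Under these assumptions, a value at or above 50 in roughly the first month is compatible with normal response.

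**The case against.** The trigger is narrow. Every on-treatment value must be 50 or more. HCV RNA is on the documentation schedule during treatment and at EoT, and patients who stop early are asked to return for EoT documentation. One later on-treatment value below 50 removes the failure-to-suppress label, as (g) and (h) show. This stands as a limit on frequency, but discretionary testing leaves gaps and the documents do not say how many.

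Other tables keep tolerability visible. SAP 4.2.5 tabulates reasons for stopping treatment and for leaving the study, and the non-response table is repeated for treatment completers, which removes (a) and (b). This also stands in part, but the repeat keeps (c) and (d), and the main table remains wrong for (a), (b) and (f).

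Several stronger readings are tempting, and the documents do not support them:
- A reader might infer that relapsers in general are filed as on-treatment failures. A relapser with an EoT value below 50 is filed correctly. Patient (d) has no documented value below 50 and so is not a shown relapser; the timing of failure is simply unknown.
- A reader might infer that every lower category is strictly subordinate. Relapse and missing SVR12 data are not, so (c) and (e) are overlaps and not removals.
- A reader might take the 2.4 to 4.8 points as the shift in the printed percentages. SAP 4.2.7.2.1 tabulates responders and non-responders together for the CP, so the natural denominator gives 0.24 points. The larger figures apply only to shares of non-responders.

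A bare cut-off at day 42 would also create an error. A patient stopped on day 35 for virological non-response, a listed reason in SAP 4.2.5, would fall under discontinuation without virologic failure.

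**Conclusion.** The point holds as a defect in a secondary descriptive table. Early adverse-event stops, early drop-outs and deaths whose only on-treatment value is an early one of 50 IU/mL or more are removed from the categories that describe them. A completer lost to follow-up is counted in two categories, and a completer with a positive post-treatment value is given a time of failure that the data do not show.

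The scale rests on the planned 417 evaluable patients and on SVR12 of 90 to 95%. That early values can be at or above 50 in responders rests on assumed viral decline. The SVR12 rate and its confidence interval are unaffected. The correction is worth making because the fault follows from the rule as written and is cheap to remove.

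**What to change.** Amend SAP 4.1.2 and 4.2.7.2.1, and note the change against protocol 9.7.3.2:

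1. Define failure to suppress as all on-treatment values at or above 50 IU/mL and either (i) at least one of them taken after the SAP's week-4 window (study day later than 42, or another minimum that the sponsor justifies), or (ii) treatment stopped with virological non-response recorded as the reason.
2. State a strict order of categories so that each non-responder is counted once, with relapse and missing SVR12 data included in that order.
3. Extend the insufficient-response category to patients with HCV RNA of 50 IU/mL or more after EoT whose only on-treatment values were early ones of 50 or more.

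With these changes (a) and (b) go to premature discontinuation, (c) to missing SVR12 data, (d) to insufficient response, (e) to relapse and (f) to death. A patient stopped on day 35 for recorded virological non-response stays in virologic failure.

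The cost is SAP wording and derivation code, with no new data. The downside is small: a few true early non-suppressors with no later test and no recorded reason would move to another category.
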